4.2 Outcome

Primary outcome:

To demonstrate non-inferiority of the DLR enabled MRI rectum technique to the current clinical protocol by:

a. Following a reduction in the acquisition time equivalent image quality is achieved (by Likert score – Median likert score DLR enabled >= clinical)

Secondary outcomes:

- a. To show agreement between the clinically relevant measurements of rectal tumours on DLR enabled vs clinical scans
- b. To describe the potential benefits of using DLR enabled protocols, including shortened acquisition times and improved imaged quality.

5 STUDY DESIGN and METHODS of DATA COLLECTION AND DATA ANALYIS

Radiographers, radiologists and physicists together will optimise the initial rectum protocol with DLR techniques enabled on healthy volunteers in the initial outset. Images will be pseudo-anonymised/anonymised and stored on the trust's Patient Archiving and Communications System (PACS) by the scanning radiographer. Data that can be used to identify the healthy volunteers will be stored in a locked spreadsheet behind the trust's firewall. This can be used to identify a volunteer whose images contain an incidental finding.

Volunteer images will be viewed on PACS, and a qualitative image quality assessment will be performed using a Likert scoring assessment undertaken by Consultant Radiologist [name]. The Likert scoring form includes scores for image quality (signal-to-noise ratio, overall image quality), and assessment of anatomical features (rectal wall, muscle fibres, intersphincteric plane and myentric plexus) as well as an overall assessment of whether or not the radiologist agrees the image is of adequate quality to report. The likert scale also includes an assessment on bowel motion. These scores will be documented on paper and stored in a locked cabinet in the medical physicists' office (MRI Annexe - ground floor) that is secured with coded pin access. These scores will contain a code to link the scores with the images acquired. No information that can be used to identify the volunteers will be recorded on these documents.

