Any images that are accessed in order to perform image quality measurements e.g. SNR, will be done so by MRI physicists ([name] and [name]). The images will be anonymised/pseudo-anonymised and exported from PACS to a trust terminal so that the anonymised/pseudo-anonymised images remain behind the trust firewall. Image quality metrics will also be calculated using an in-house Matlab 2022b script written by MRI physicists ([name] and [name]).

Once a DLR enabled rectum protocol has been established, patients who meet the inclusion criteria will be invited to take part in this study. If they give informed written consent, their routine scans will be appended with the DLR sequences. A maximum of 15 mins of sequences will be added. Their participation in this study will be noted on the trust's Radiology Information System (RIS)/Soliton. Further detail relating to the inclusion and exclusion criteria for participants can be found in section 7 of this study protocol.

Acquired images will be archived to PACS by the scanning radiographer and will undergo qualitative assessment, the same Likert scoring employed with the healthy volunteers, by [name]. Again, these scores will be documented on paper and stored in a locked cabinet in the medical physicists'

office that is secured with coded pin access. These scores will contain a code to link the scores with the images acquired. No information that can be used to identify the patients will be recorded on these documents. Statistical analysis of the Likert scores will be carried out using a two-tailed pairwise Wilcoxon signed-rank test.

Additionally, bio-marker measurements will also be carried out by the reporting radiologist with statistical analysis of the bio-marker measurements between the pre-existing and DLR enabled sequence for the patient sample group also performed by the MRI physicists ([name] and [name]).

Conclusions regarding image quality and the validity of DLR being suitable for clinical rectum protocols will be made by [name], [name] and [name].

Any other hard copies of data/notes will be stored in the locked cabinet within the locked medical physicists' office.

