What stone or controls are you taking to usinjusiae viake to universe.				
	What steps or controls are you taking to minimise risks to privacy? Please tick those which apply and provide details of how each is ensured			
TIOGOC GON GIOSC WITICIT A	Please tick those which apply and provide details of now each is ensured			

- 1. Risks to individual privacy are minimal
- 2. Personal data is pseudonymised
- 3. Encryption used in transfers of patient data.
- 4. Information compliance training for staff has been completed data protection, information security, FOI
- 5. Adherence to privacy by design principles
- 6. Special category personal data is not used
- 7. Participants opt out at any stage of the research
- 8. Personal data kept in the UK
- 9. Research is not used to make decisions directly affecting individuals
- 10. Short retention limits
- 11. Restricted access controls

- 1. Information is only accessed by study delegates.
- Images transferred from PACS
 can be pseudo-anonymised and
 stored in trust PCs. This will be
 enabled when images are
 transferred.
- All staff with access to patient and volunteer participant information access have up to date information governance MAST training
- 4. The radiographers/radiologists involved with the additional scans are the same staff members who perform the routine clinical scan already undergone by the patient.
- 5. CRF will be coded so that it does not include patient information.
- 6. Special category personal data will not be collected or included for the study.
- 7. Contact details and guidance on how to opt out is included on the Patient Information Sheet (PIS), as well as a withdrawal form.
- 8. Only anonymised MR images would be shared outside of the trust, eg for publication. No patient identifying information will be shared outside of the trust.
- Research protocols are only assessed alongside routine clinical scans by reporters, not replacing clinical scans. Any clinical decision made for the patient will be made on clinical scans.
- All data will be stored on password locked staff computers and only accessible by study delegates.

			_	
			11. No patient data would be stored	
			without reason for doing so and deleted once it has been used.	
How long will you need to	hold the personal date	a for after the st		
	· · · · · · · · · · · · · · · · · · ·		s complete patients' personal information	
will no longer be useful ar	· · · · · · · · · · · · · · · · · · ·	•	s complete patients personal information	

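### Likert scores and tumour measurements on the paired clinical and DLR series are read with no masking, random order or separation, which leaves the primary and agreement outcomes open to reader bias of unknown direction

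*Protocol*

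**What the plan says.** **Outcomes.** Protocol section 4.2 makes a Likert image-quality score the primary outcome. Success means that the DLR median is at least the clinical median. Agreement of tumour measurements between the two techniques is a secondary outcome.

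**Readers.** In section 5 the volunteer images have a "Likert scoring assessment undertaken by Consultant Radiologist". Patient images then receive "the same Likert scoring employed with the healthy volunteers", again from a single named person. For the tumour measurements, "bio-marker measurements will also be carried out by the reporting radiologist", and the existing and DLR sequences are then compared statistically.

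**Involvement in development.** Section 5 opens with "Radiographers, radiologists and physicists together will optimise the initial rectum protocol". Objective ii in section 4.1 adds repeated review and re-optimisation with input from radiologists.

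**Order of acquisition.** For consenting patients, "their routine scans will be appended with the DLR sequences", so DLR always comes second.

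**Coding.** Of the score sheets, section 5 says: "These scores will contain a code to link the scores with the images acquired". Its stated purposes are linkage and keeping participant identity off the paper.

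**The concern.** The primary outcome is a judgement on a form. Unless the reader is kept from knowing which series is which, any expectation about DLR goes straight into the score. A radiologist who has helped to tune the protocol may well hold such an expectation.

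The agreement outcome has a different weakness. If the same person measures a tumour on both series, and the first value is known or remembered, the second measurement is not independent. The comparison then partly measures recall.

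The protocol's own background makes this consequential. It stresses accurate tumour size for staging, describes the failure modes of DLR as poorly understood, and notes that abnormalities have been lost on reconstructed images. Unmasked paired reading weakens the check on that risk.

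Who reads, with what knowledge and in what order is a matter of data collection, which section 5 sets out to describe. A statistical analysis plan could not remove the effect once the readings exist.

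**Working it through.** **1. The plan's own figure.** Section 7.2.1 gives 24 pairs for a two-sided Wilcoxon signed-rank test with dz = 0.8, alpha 0.05 and power 0.95. With a normal parent the efficiency is 3/π:
- effective n = 24 × 3/π = 22.92
- noncentrality = 0.8 × √22.92 = 3.83
- df = 21.92, critical t = 2.074
- power = 0.955 (23 pairs give 0.947)

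So 24 reproduces. Then 24 × 2 / (1 − 0.20) = 60 patients, and 60 + 15 = 75. The point below does not alter these numbers. Each half of the DLR protocol is compared on 24 pairs.

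**2. Search for safeguards.** Section 5 and the rest of the protocol contain no masking of series type, no random reading order, no interval between paired reads and no measurement made without sight of the first. The only reference to blinding is in section 1, about a cited lumbar spine study. Pseudonymisation and coding conceal the participant, not the reconstruction.

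**3. Effect on the Likert rule (assumed values).** The protocol gives no SD and no bias size. As a proxy for the section 4.2 rule, take the median paired difference (DLR minus clinical) being at least 0, with 24 pairs and normal differences, in units of their SD. The sample median then has a standard error of about 0.2485 (by simulation). The pass rate is approximately Φ((true difference + reader shift) / 0.2485). With DLR truly worse by 0.4 SD:

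| Reader shift (SD) | Net mean | Pass rate |
|---|---|---|
| −0.2 (sceptical) | −0.6 | Φ(−2.41), below 1% |
| 0 | −0.4 | Φ(−1.61), about 5% |
| +0.2 | −0.2 | Φ(−0.80), about 21% |
| +0.4 | 0 | Φ(0) = 50% |

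The planned test responds in the same way. With DLR truly worse by 0.8 SD, simulation of the two-sided Wilcoxon test with 24 pairs detects this 96% of the time under neutral reading. With a 0.4 SD preference for DLR it detects it 45% of the time.

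**4. Effect on agreement (assumed values).** Let the independent readings be m1 and m2. If the second moves halfway to the first, the recorded value is m2 + 0.5(m1 − m2), and the recorded difference is 0.5(m2 − m1). Both the mean difference and its SD halve. For an assumed SD of 4 mm, the 95% limits of agreement around the mean difference go from ±1.96 × 4 = ±7.8 mm to ±1.96 × 2 = ±3.9 mm. Expressed instead as correlated reading error, the limits shrink by √(1 − ρ): to 71% at ρ = 0.5, 50% at ρ = 0.75 and 32% at ρ = 0.9.

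**The case against.** The strongest reply is that the protocol is silent on how the reading is done, and silence does not prove bias. That stands: the outcomes are open to bias, and nothing shows that they are biased. A reader might infer four stronger things, none of which the documents support.

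- **The bias favours DLR.** No expectation is documented. The background is cautious about DLR, so a sceptical reader is possible. DLR is always acquired last, and section 7.2.1 foresees movement confined to the DLR scan, which could count against it.
- **Side-by-side reading is specified.** The data protection assessment in Appendix 3 says "Research protocols are only assessed alongside routine clinical scans by reporters, not replacing clinical scans". That sentence answers a question about decisions affecting individuals and makes clear that clinical decisions rest on clinical scans. It is not a reading protocol, and it could remain true under masked research reads.
- **One person scores, tunes and reports.** Names are removed, so this cannot be confirmed, and section 3 speaks of radiologists in the plural for Likert scoring. Nor does section 5 say that the clinical report comes first or that the first measurement is visible during the second.
- **False non-inferiority rises from 2.5% to 32%.** This follows from a +0.2 point shift with a −0.5 point margin, an SD of 0.625 and a one-sided 0.025 t-test on 24 pairs. The protocol contains none of these except the 24. Its rule compares medians and its test is a two-tailed Wilcoxon. A shift of −0.2 in the same formula gives about 0.03%.

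The omission itself is untouched by these replies: no safeguard is stated, and the reading plan can be followed to the letter without one.

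**Conclusion.** The point holds as a design weakness in section 5. A subjective primary score and a same-reader agreement outcome are collected with nothing to stop knowledge of the series, or of the first reading, from entering the second. The two mechanisms differ. Expectation shifts the Likert comparison in an unknown direction, whereas anchoring can only make agreement look better than it is.

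The sizes are illustrations. The move from about 5% to 21% or 50% assumes a true deficit of 0.4 SD, a preference of 0.2 or 0.4 SD, continuous normal differences, and the median paired difference as a stand-in for the stated rule. Discrete Likert scores with ties would give other figures. The halved limits rest on an assumed halfway pull. They show that modest reader effects could decide the outcome, not that they will. It should be settled before patient images are read, because later analysis cannot repair it.

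**What to change.** In section 5, state that:

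- the same reader or readers score coded series one at a time, with series name, acquisition time and reconstruction label hidden;
- the order is random and computer-generated, and the two series of a patient are read in separate sessions, at an interval set by the team;
- research tumour measurements on both series follow the same scheme, without sight of the other measurement or the clinical report;
- the series key is opened only after scores and measurements are locked.

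Routine clinical reporting is unaffected, and the Appendix 3 sentence need not change. No extra scan, patient or reader is required, and the 24 pairs per half-protocol stand.

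The costs are a read list and de-labelled series, radiologist time for separate research measurements in up to 60 patients of an unfunded study, and a short delay. Section 5 already has physicists exporting pseudonymised images, but for image-quality metrics. Whether that route suits diagnostic reading and measurement would need checking. Masking may be imperfect, because DLR images can be recognisable by appearance. It would reduce the risk without removing it.

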6 STUDY SETTING

This is a single centre study at St George's Hospital with three MRI scanners that each have up-to-date software versions with DLR functionality. Healthy volunteers will be recruited for initial optimisation of the DLR enabled rectum protocol and will be recruited from within St George's Hospital's Medical Physics and Clinical Engineering (MPCE) group via an email on the joint mail base.

It will be explained to volunteers that images will be reviewed in the context of image quality assessment. In the event of an incidental finding, the volunteer's GP will be notified. A volunteer will not be scanned if they do not provide details of their GP, NHS number, and do not give consent to being scanned. Any volunteer that is vulnerable, not an adult, is/may be pregnant or has any other contraindications to MRI will be immediately excluded from this study. All volunteer images will be stored on PACS and accessed only by [name], [name], [name] or any other delegate listed on the delegation log. These images will be stored for up to 10 years following completion of the study, unless a participant wishes for them to be deleted at an earlier date.

Validation will need to be carried out on adult patients referred to St George's Hospital's General Radiology MRI department for an MRI pelvis scan for a rectum study. This research setting is appropriate since there are approximately 200 patients who are referred for a pelvis MRI each year, with patients also having follow-up scans throughout their care.

Potential participants will be identified by the Radiology Information System (RIS) and their suitability will be assessed. Any patient that is vulnerable, not an adult, is/may be pregnant or has any other contraindications to MRI will be immediately excluded from this study.

Once a patient's suitability has been approved, they will be invited to take part by post and a participant information sheet (PIS) will be provided (e.g. in person, via email or post). The potential participant will be provided with the contact details of the researchers ([name] and [name]) if they have any questions.

If the patient wishes to participate in this study, they will be provided with the PIS and given another opportunity to read it and ask questions on the day of their scan before written consent is obtained. This consent will be recorded on RIS/Soliton. The participant will then continue through the safety checks, which will be the same process as their referred scan (MRI screening questionnaire and changing into patient gowns). These will be performed by St George's Hospital MRI radiographers.

Participants will be setup by the radiographers and have the same patient setup as the routine pelvis MRI. This will include being placed in the MRI scanner (Siemens Magnetom Sola 1.5T or Siemens Magnetom Vida 3T) either in head-first-supine or feet-first-supine position with a single, multi-channel anterior receiver coil and the built in spine coil activated. Participants will also spend up to an additional 15 minutes of scanning due to the DLR enabled sequences being appended to the study.

All scanning will be carried out by the scanning radiographer. Contrast will never be given as part of this protocol. Participants will have no further responsibility in this study once their scan is complete.

7 SAMPLE AND RECRUITMENT

7.1 Eligibility Criteria

This section sets out with precise definitions of which participants are eligible for this study, defining both inclusion and exclusion criteria.

7.1.1 Inclusion criteria

Staff in the Medical Physics and Engineering group, plus adult patients that have been referred to St George's Hospital General Radiology MRI department for an MRI pelvis study and able to withstand up to an additional 15 minutes in the MRI scanner will be considered for participation in this study.

The ability for volunteers and patients participating in this study will not be dependent on:

- Gender.
- Ethnicity.
- Socio economic grouping.
- Clinical condition.
- Location.

7.1.2 Exclusion criteria

Any volunteer that is not an adult; and is/or may be pregnant, will be excluded from this study.

Any patient that cannot give informed written consent, cannot complete a screening questionnaire, is not an adult; has not been referred for an MRI pelvis scan for a rectum study at St George's Hospital General Radiology MRI department as an outpatient; is an at-risk patient; and is/or may be pregnant, will be excluded from this study.

Non-English speakers will be excluded from this study as informed consent cannot be guaranteed and questions the participants may have may not be satisfactorily answered.

7.2 Sampling

7.2.1 Size of sample

We aim to recruit a maximum of **75** participants in this study, which includes **15** healthy volunteers and **60** patient participants (see GPower calculation below).

GPower 3.1.9.7 was used to undertake a power analysis calculation by selecting a Wilcoxon signed-rank test (matched pairs), with the following inputs:

- Two tails
- Normal distribution
- Large effect size (dz) of 0.8
- A error probability of 0.05
- Power (1-β error probability) of 0.95

This results in a sample size of 24.

However, the actual number of patient participants required will be different to the sample size calculated by GPower as it is dependent on how effective DLR techniques are at reducing acquisition times.

A conservative estimate for the reduction in the total acquisition time is approximately 50%. Since the routine protocol is 23 minutes and 57 seconds, decreasing the acquisition time by 50%, and considering only the sequences that can have DLR techniques enabled, results in a DLR enabled protocol of 11 minutes and 46 seconds.

However, as the rectum MRI booking slot is a maximum of 30 minutes, the routine and DLR enabled protocol, which combined is 35 minutes and 43 seconds, cannot be acquired in one booking slot. Therefore, the first half of the DLR enabled protocol will need to be appended to 24 patient participant scans and the second half of the DRL enabled protocol will need to be appended to another 24 patient scans. Increasing or exceeding the minute booking slot cannot be exceed (as stipulated by [name] (Superintendent of General Radiology MRI).

Additionally, patient participants may drop out of the study, whilst other patients may have to be excluded following their scan. An example of the latter may be that the patient had significant movement in the DLR enabled scan, which did not occur during the routine part of the scan. This dropout rate is estimated to be **20%**, as indicated by [name] (Superintendent of General Radiology MRI).

The need to double the number of participants due to logistical factors related to the booking slot, a dropout rate of 20%, as well as the need to scan approximately 3 volunteers results in an estimated maximum sample size of 75 participants:

 $((24 \times 2) \div (1 - 20\%)) + 15 = 75$ participants.

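### The 24 pairs per protocol half come from a difference test at dz 0.8, so the 0.95 in section 7.2.1 is not the power for the non-inferiority primary outcome

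*Protocol*

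**What the plan says.** **Primary outcome (Protocol, section 4.2).** The aim is "To demonstrate non-inferiority of the DLR enabled MRI rectum technique to the current clinical protocol by" a criterion on Likert image quality after a shorter acquisition: "Median likert score DLR enabled >= clinical". No non-inferiority margin and no SD of the paired differences are stated.

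**Analysis (Protocol, section 5).** "Statistical analysis of the Likert scores will be carried out using a two-tailed pairwise Wilcoxon signed-rank test".

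**Sample size (Protocol, section 7.2.1).** The calculation was made by "selecting a Wilcoxon signed-rank test (matched pairs), with the following inputs". It is two-sided, assumes a normal parent for the paired differences, and takes a "Large effect size (dz) of 0.8" together with alpha 0.05 and power 0.95. The outcome is then given: "This results in a sample size of 24". Because the booking slot cannot hold both full protocols, one half of the DLR protocol is added for 24 patients and the other half for another 24. The total of 48 is divided by 0.8 for dropout to give 60 patients, and 15 volunteers bring it to 75.

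**The concern.** The sizing inputs describe a test that succeeds when the two sets of scores are shown to differ, in either direction, and the assumed difference is large. The primary claim succeeds when DLR is shown not to be worse. These are different hypotheses. Power for the second depends on how much loss would be tolerated and on any true difference between the protocols, and no tolerated loss enters the calculation.

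The 0.95 is the only power figure in the document, so a reader will take it as the study's assurance on its primary outcome. That matters here. Section 1 says that abnormalities have been missed on deep-learning reconstructions and that validation must precede clinical use. Section 3 says that the patient's pathway depends on biomarkers measured on these images.

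**Working it through.** **Inputs from the protocol.** Wilcoxon signed-rank test, matched pairs, normal parent distribution, two tails, dz = 0.8, alpha = 0.05, power = 0.95, n = 24 per half (all section 7.2.1). Here dz is the mean paired difference divided by the SD of the paired differences.

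**Inputs assumed.** The protocol gives no margin and no SD. Margins m are therefore assumptions, in SDs of the paired difference, shown as a range. The one-sided alpha is also an assumption: 0.025, with 0.05 as an alternative.

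**Step 1: reproduce the 24.** For a normal parent, the asymptotic relative efficiency of the signed-rank test is 3/π = 0.955.

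- Effective size: n′ = n × 3/π = 24 × 0.955 = 22.92, with n′ − 1 = 21.92 degrees of freedom.
- Noncentrality: dz × √n′ = 0.8 × √22.92 = 3.83.
- Two-sided 5% critical value: t = 2.074.
- Power from the noncentral t: 0.955 at n = 24, and 0.947 at n = 23.

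So 24 is the smallest n that reaches 0.95. Simulating the signed-rank test itself (20,000 runs, normal differences, dz 0.8, n = 24) gives 0.956. The protocol's figure is correct for a difference test.

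**Step 2: what that test does if image quality is equal.** With a true difference of 0 it rejects about 5% of the time, which is its alpha. The 0.95 therefore says nothing about the case in which the two protocols are equally good.

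**Step 3: non-inferiority with the same 24 pairs.** Same method, one-sided, with noncentrality (m + δ) × √22.92, where δ is the true DLR advantage in SDs. For example, with m = 0.5 and δ = 0 the noncentrality is 0.5 × 4.787 = 2.39, against a critical value of 2.074 at one-sided 0.025. Power is 0.63.

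| Assumed margin (SD), δ = 0 | Power, one-sided 0.025 | Power, one-sided 0.05 |
|---|---|---|
| 0.3 | 0.28 | 0.40 |
| 0.4 | 0.45 | 0.58 |
| 0.5 | 0.63 | 0.75 |
| 0.6 | 0.78 | 0.87 |
| 0.8 | 0.955 | 0.98 |
| Margin for 95% power | 0.79 | 0.71 |

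**Step 4: let the true difference vary.** Only the sum m + δ matters. At one-sided 0.025:

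- m = 0.5, δ = +0.2 (sum 0.7): 0.89.
- m = 0.5, δ = +0.3 (sum 0.8): 0.955.
- m = 0.5, δ = −0.1 (sum 0.4): 0.45.

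So 24 pairs have 95% power for non-inferiority whenever margin plus true advantage is about 0.8 SD, and less when it is smaller.

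Like the protocol's own calculation, these figures treat the paired differences as normal. Likert differences are ordinal and tied, so the figures are approximate.

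**The case against.** The strongest reply is that sizing and analysis agree with each other. Section 7.2.1 powers the two-tailed signed-rank test that section 5 names, and the number is right. The 0.95 appears only as an input to that calculation, and the protocol nowhere says in words that it has 95% power for non-inferiority. This stands. The mismatch is between both of those sections and the wording of the primary outcome in 4.2, and the fault is a sample size not derived from the primary hypothesis.

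Second, 0.8 SD could serve as a margin, and then 24 pairs would be enough. Numerically that is so. But the protocol presents 0.8 as a large effect to be detected, not as a loss that may be accepted, and offers no justification for it as a margin.

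Third, a true difference of 0 may be pessimistic. The study hypothesis and objective (i) allow for better image quality, and section 1 cites higher signal-to-noise and contrast with DLR in another application. This also stands, which is why the power figures cannot be quoted for a zero difference alone. It does not rescue the 0.95, because no advantage of a stated size is assumed anywhere.

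A reader might go further and infer that a non-significant Wilcoxon result will be taken as proof of non-inferiority, so that a small sample makes success easier. The protocol does not support that. Its stated criterion is on the medians, and it does not say how the test result feeds the conclusion.

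**Conclusion.** The point holds. The stated 0.95 is the power to detect a 0.8 SD difference, not the power for the primary claim. Nor does it describe how often the criterion on observed medians would be met. The size of the shortfall cannot be fixed from the document, because it depends on a margin and an SD that the protocol does not give. Over assumed margins of 0.3 to 0.6 SD it runs from 28% to 78% (one-sided 0.025, no true difference).

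This does not show that 24 pairs are too few. A justified margin near 0.8 SD, or a narrower one combined with a credible DLR advantage, would make them sufficient. What is wrong as written is that the only power figure given belongs to a different hypothesis from the primary outcome.

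**What to change.** Keep the sample size and change the text:

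1. In section 7.2.1, state that 24 pairs give 95% power to detect a difference of 0.8 SD of the paired differences, and that this is not the power for non-inferiority.
2. In section 4.2, have the investigators pre-specify a non-inferiority margin on the Likert scale and an assumed SD of the paired differences, with reasons for both.
3. In section 7.2.1, report the non-inferiority power that 24 pairs per half deliver for that margin, with the one-sided alpha named, once for a true difference of 0 and once for a plausible DLR advantage.

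The cost is a rewritten paragraph, the work of agreeing a margin, and a less favourable stated power unless a margin near 0.8 SD can be justified. No extra patients are needed if the investigators accept and disclose that power. If they instead wanted 95% power at a narrower margin, n would have to rise. At an assumed 0.5 SD margin with no true difference (one-sided 0.025), 57 pairs per half are needed, which is 2 × 57 ÷ 0.8 = 142.5, so 143 patients against the 60 planned.

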2 RATIONALE

One of the disadvantages in MRI is that acquisition times can be lengthy, making it likely that patient movement whilst in the scanner will affect image quality and making it more difficult for patients to complete their MRI scan (Hollingsworth et al. 2015). In recent years, waiting lists of patients referred for MRI have also been at an all-time-high as a result of the COVID-19 pandemic (GOV.UK, 2023).

To tackle this backlog, manufacturers have developed Artificial Intelligence (AI) image reconstruction (DLR) techniques that compensate for the poor image quality that results when using higher accelerating/parallel imaging factors during MRI scanning (Magnetom Flash, 2021). This also has the potential to improve patient compliance.

These DLR techniques are still relatively new and require a number of resources including radiographer, radiologist and clinical scientist support to optimise the technique. Consequently, implementation across the NHS has been slow and has therefore not yet been validated on rectum MRI protocols. Therefore, the aim of this study is to demonstrate that DLR techniques can be implemented in rectum MRI protocols, as well as provide recommendations for its implementation.

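### The only example of a post-scan exclusion drops patients who moved on the DLR scan but not the routine scan; applied as written, it tilts the paired Likert comparison towards DLR

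*Protocol*

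**What the plan says.** Protocol section 7.2.1 inflates the patient sample for losses of 20%. Besides dropouts, it expects that "other patients may have to be excluded following their scan", and it illustrates this with a case where "the patient had significant movement in the DLR enabled scan, which did not occur during the routine part of the scan". No other example is given. The exclusion does not appear among the exclusion criteria in section 7.1.2.

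The comparison affected is the primary one. Section 4.2 sets out "To demonstrate non-inferiority of the DLR enabled MRI rectum technique to the current clinical protocol by" means of Likert image quality, with the criterion "Median likert score DLR enabled >= clinical". Section 5 analyses the scores with a "two-tailed pairwise Wilcoxon signed-rank test". On acquisition, section 5 says of consenting patients that "their routine scans will be appended with the DLR sequences". Section 2 gives lengthy acquisition as a reason for movement, "making it likely that patient movement whilst in the scanner will affect image quality".

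**The concern.** In a paired comparison, an exclusion that depends on the quality of one member of the pair is selection on the outcome. The example removes a pair when the DLR image is degraded by movement and its comparator is not. Those pairs are likely to score lower on DLR. The mirror case, movement on the routine scan only, is likely to score lower on the routine protocol, and the example does not remove it. Applied as written, the exclusion therefore moves the expected result towards DLR.

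The direction matters because the study sets out to show that DLR is no worse. A selection that removes unfavourable pairs makes the data less able to show that DLR is worse. It also hides how often the added DLR acquisition gives an image unfit to report, although adequacy for reporting is an item on the section 5 scoring form.

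**Working it through.** **1. The plan's own figures.** Section 7.2.1 gives a two-tailed Wilcoxon signed-rank test, normal parent, dz = 0.8, alpha 0.05, power 0.95 and n = 24. Using the asymptotic relative efficiency method (effective n = N × 3/π, noncentral t):

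- N = 23 gives power 0.947.
- N = 24 gives power 0.955, so 24 is reproduced.
- Patients: (24 × 2) ÷ (1 − 0.20) = 60. Total: 60 + 15 = 75. Both are reproduced.

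The point changes none of these figures.

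**2. Room for exclusions.** 20% of 60 is 12 patients, or 6 of 30 in each half-protocol group. This covers dropouts and post-scan exclusions together, and the split is not stated.

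**3. Illustration.** The protocol gives no movement rate and no score distribution, so these inputs are assumptions:

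- 30 pairs in one half-protocol group.
- Routine score 3, 4 or 5 with probability 0.2, 0.5, 0.3.
- DLR score equal to routine plus −1, 0 or +1 with probability 0.2, 0.6, 0.2, capped at 5.
- DLR-only movement in a fraction m of patients, with DLR then scoring 2 points below routine.
- m = 5%, 10% or 20%.

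The mean difference (DLR minus routine) can be found by hand. Without movement, the cap alone costs 0.3 × 0.2 × 1 = 0.06, so the mean is −0.06. With all pairs it is (1 − m)(−0.06) + m(−2):

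- m = 5%: −0.057 − 0.100 = −0.157
- m = 10%: −0.054 − 0.200 = −0.254
- m = 20%: −0.048 − 0.400 = −0.448

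After the one-sided exclusion it returns to −0.06 whatever m is. A simulation of 4,000 trials per row agrees and adds the two decision quantities. The median criterion is taken as the median of the DLR scores being at least the median of the routine scores.

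| DLR-only movement | Mean difference, all pairs | Mean difference, after exclusion | Median criterion met, all pairs | Median criterion met, after exclusion | Test shows DLR worse, all pairs | Test shows DLR worse, after exclusion |
|---|---|---|---|---|---|---|
| 5% | −0.16 | −0.06 | 0.97 | 0.98 | 0.19 | 0.06 |
| 10% | −0.25 | −0.06 | 0.94 | 0.98 | 0.38 | 0.06 |
| 20% | −0.45 | −0.06 | 0.77 | 0.98 | 0.78 | 0.06 |

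Simulation error on each probability is at most √(0.25 ÷ 4000) ≈ 0.008.

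**4. Reading the table.** The exclusion shifts the mean towards DLR by about 0.10, 0.19 and 0.39 points. The median criterion hardly notices at 5% or 10%. The signed-rank test loses most of its chance of showing DLR worse at every rate. The 20% row is an upper edge, because it spends the whole allowance on DLR-only movement and leaves none for dropout.

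**The case against.** **Status of the text.** The sentence sits in the sample-size section, is worded as a possibility, and is offered as an example. It does not forbid excluding the mirror case, and a statistical analysis plan may define analysis sets. This stands as a limit: the criticism is of the one-sided example as written, not of missing analysis detail. But it is the only example the protocol gives, and following it produces the selection described.

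**Scan order.** A reader might infer that the excluded scans are all DLR failures. The documents do not support that. The DLR block is appended to a routine protocol that section 7.2.1 puts at 23 minutes 57 seconds, and section 2 links movement to long acquisition. Some DLR-only movement may therefore come from time in the scanner. Keeping every pair could then penalise DLR for being scanned last. This stands, and it is why an all-pairs set is not the only acceptable primary analysis. It does not justify removing pairs in one direction only.

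**Movement as a scored item.** A reader might also infer that the exclusion trigger is itself scored, because "The likert scale also includes an assessment on bowel motion". Bowel motion is not gross patient movement, and the protocol does not equate them. The argument does not need this: the form scores overall image quality, which gross movement can lower.

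**A reversed conclusion.** A reader might infer that the exclusion turns an inferior result into a non-inferior one. That is not shown in general on the stated median criterion. Take a worse/same/better split of 30/45/25%. Removing 10 points from the worse group gives 20/90, 45/90, 25/90 = 22.2/50/27.8%. Removing 20 gives 10/80, 45/80, 25/80 = 12.5/56.25/31.25%. The net balance moves from −5 to +5.6 and +18.75 points, but the median paired difference is zero in all three. In the table above, only the 20% edge moves the median criterion much.

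**Conclusion.** The point holds in a limited form. Applied as written, the example in section 7.2.1 selects against pairs likely to be unfavourable to DLR and shifts the primary Likert comparison towards DLR. The direction follows from the wording together with the expectation that gross movement lowers the score.

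The size is unknown. It depends on the movement share of the 20% allowance and on how much movement costs in score, and the protocol gives neither. Under the assumed 5% to 20% rates and 2-point loss, the main damage is to the signed-rank test's ability to show DLR worse. The effect on the median criterion is small at 5% to 10%. An unknown part of any DLR-only movement may be due to scan order.

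**What to change.** Before patient scans are scored, amend section 7.2.1 and the analysis text in section 5:

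- Replace the one-sided example with a single pre-defined movement rule that applies equally to movement on either scan, judged without knowledge of technique or Likert scores.
- Report the number of motion-degraded or non-reportable scans by technique.
- Present the Likert comparison in two ways: all pairs with both acquisitions, scored as acquired; and the same comparison after the symmetric exclusion. State in advance which is primary.

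The cost is a change of wording plus one extra analysis, with no added patients or scan time. The downside is that the all-pairs analysis may understate DLR quality because DLR is scanned last. Setting it beside the symmetric analysis shows how far the result depends on movement.
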